#### **12.4.2 Laboratory Assessments**

All laboratory-based data will be presented as listings of all values as well as abnormal results judged to be clinically significant, which will also be reported as AEs. Numeric summaries of all observed and change from baseline laboratory evaluations will be provided by visit and treatment group, including chemistry, hematology, and urinalysis results. No inferential comparisons are planned.

#### **12.4.3 Vital Signs**

Numeric summaries of all observed and change from baseline vital signs will be provided by time point and treatment group, including blood pressure, heart rate, and temperature. No inferential analyses are planned for vital signs.

#### **12.4.4 ECGs and Physical Examination**

Physical examination data and changes will be presented as listings. ECG results will be presented as listings and summarized by treatment group and visit based on incidence of clinically significant abnormalities. No inferential comparisons across treatment groups are planned.

#### **12.4.5 Other Assessments**

Other collected data not specifically mentioned, including physical examinations and protocol deviations, will be presented in subject listings.

#### **12.4.6 Safety of Vesigenurtacel-L (Phase 1 and Arm 4 of Phase 2 Only)**

Safety is defined as the number of adverse events (AE)/serious adverse events (SAE) in patients receiving vesigenurtacel-L.

#### **12.4.7 Safety of the Combination of Vesigenurtacel-L and BCG (Arms 1, 2, and 3 of Phase 2 Only)**

Safety is defined as the proportion of AE/SAE in patients receiving the combination of vesigenurtacel-L and BCG compared to the proportion of AE/SAE in patients receiving the combination of placebo and BCG.

### **12.5 Efficacy Analysis (Phase 2)**

All efficacy analyses will be based on the ITT population unless otherwise specified.

#### **12.5.1 Primary Efficacy Analysis**

##### **12.5.1.11-year Disease-Free Survival (1-yr DFS)**

One-year disease-free survival will be defined as the proportion of patients who are free from recurrent disease, progressive disease, and alive one year after the date of randomization/treatment assignment (Arm 4).

For the primary efficacy evaluation, disease-free survival at one year between the experimental groups and the control will be presented as the absolute difference in proportions, as well as the OR, with the associated 95% CI.

#### **12.5.2 Analysis of Secondary Efficacy Parameters**

The Secondary Efficacy Parameters will be analyzed using Kaplan-Meier time-to-event methodology.

##### **12.5.2.1 Time to Recurrence**

Defined as the time from randomization to recurrence of disease to the same extent (stage and grade) as screening.

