## **10.0 ASSESSMENT OF EFFICACY**

### **10.1 Evaluation of Disease**

Monitoring for disease status via cystoscopy, cytology, and biopsy if indicated, will be conducted every 3 months during treatment and follow up for 2 years then every 6 months for up to a year per SOC. Disease-free status is defined as no evidence of disease, which in turn is defined as negative cytology, negative cystoscopy, and negative biopsy if clinically indicated.

Recurrence is defined as disease that has recurred to the same extent of disease (i.e. same stage/severity) or to a lower stage/severity of disease compared to screening.

Persistent disease is defined as evidence of CIS disease by 6 months for patients with CIS at screening.

Progression is defined as an increase in T stage from CIS or Ta (at screening) to T1 (lamina propria invasion), development of T2 or greater or lymph node (N+) disease or distant metastasis (M1), or an increase in grade from low to high per the IBCG recommendations.

The stage of disease at the time of recurrence or progression will be captured to distinguish between recurrence to the same extent of disease as at screening (i.e. the same stage/severity) versus recurrence to a lower stage/severity of disease at screening versus persistent disease for CIS versus progression.

The date of confirmation of recurrence or progression is defined as the earliest date on which the diagnosis had been made based on the findings of cystoscopy, urinary cytology, or some other diagnostic imaging technique regardless of whether the patient continues treatment. For the purpose of clarity, in the situation where a patient with CIS documented at screening has evidence of CIS at the 3-month assessment, continues treatment, and still has evidence of CIS at 6 months, that patient will be assumed to have persistent disease from the date of randomization.

For intermediate-risk patients (i.e. without CIS) who have evidence of disease at the 3-month assessment, continue treatment, and still have evidence of disease at 6 months, the date of recurrence would be the date of the 3-month assessment.

If requested, the cystoscopy and cytology reports and images may be appended to the ECRF with all patient identifier information removed and the study site and patient study number written on the report, which is to be signed and dated by the investigator.

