##### **12.5.2.2 Time to Progression**

Defined as the time from randomization to progression of disease to a greater stage.

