7.2 Secondary Efficacy Analyses

For time-to-event endpoints (e.g. DFS, OS), Kaplan-Meier / product limit method will be used to estimate the survival distributions over time, and to estimate median time to event. Where appropriate, inference for time-to-event endpoints will be assessed using the Log-rank test statistic, and the treatment effect will be estimated using Cox proportional hazards model. The assumption of proportional hazards will be assessed graphically.

The following will be analysed using Kaplan-Meier time-to-event methodology:

- Time To Recurrence, defined as the time from randomization to recurrence.
 - Recurrence is defined as disease that has recurred to the same extent of disease (ie same stage / severity) or to a lower stage/severity of disease compared to screening.
 - If recurrence has not occurred in a patient, the date of last disease assessment will be used as the timepoint for censoring.
 - The analysis will be repeated in an exploratory manner where recurrence is defined as only those recurrences to the same extent of disease (or greater) as screening.

- Time To Progression, defined as the time from randomization to progression.
 - Progression is defined as an increase in T stage from CIS or Ta (at screening) to T1 (lamina propria invasion), development of T2 or greater or lymph node (N+) disease or distant metastasis (M1), or an increase in grade from low to high per the IBCG recommendations..
 - If progression has not occurred in a patient, the date of last disease assessment will be used as the timepoint for censoring.

- Disease-Free Survival, defined as the time from randomization to recurrence or progression.
 - If a patient has recurred or progressed, then the first date the recurrence or progression has occurred will be used as the timepoint for the event.
 - If a patient has neither recurred nor progressed, then the date of last disease assessment will be used as the timepoint for censoring.

- Overall Survival, defined as the the time from randomization to death.
 - If a patient is still alive, then the patient will be censored on the date of most recent date known alive.
 - If a patient is lost to follow up, then the patient will be censored on the date last known alive.

- Time to cystectomy, defined as the time from randomization to cystectomy.
 - If a patient has not undergone cystectomy, the patient will be censored on the date of last disease assessment.

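### Protocol 12.5.2.1 and 12.5.2.2 define recurrence and progression more narrowly than section 10.1 and SAP 7.2, so two types of event are missed if they are followed literally

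*Protocol*

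**What the plan says.** The protocol defines the two events twice.

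- Protocol 10.1 (Evaluation of Disease): "Recurrence is defined as disease that has recurred to the same extent of disease (i.e. same stage/severity) or to a lower stage/severity of disease" than at screening. Its definition of progression covers CIS or Ta advancing to T1, T2 or higher, nodal or distant disease, "or an increase in grade from low to high per the IBCG recommendations".
- Protocol 12.5.2.1, on time to recurrence: "Defined as the time from randomization to recurrence of disease to the same extent (stage and grade) as screening".
- Protocol 12.5.2.2, on time to progression: "Defined as the time from randomization to progression of disease to a greater stage".

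The SAP sides with section 10.1. Sections 2.1 and 7.2 take recurrence as disease that has "recurred to the same extent of disease (ie same stage / severity) or to a lower stage/severity of disease compared to screening", and both include the grade change in progression. In SAP 7.2 a restricted recurrence definition appears only as a secondary look, with the analysis "repeated in an exploratory manner where recurrence is defined as only those recurrences to the same extent of disease (or greater") relative to screening. Protocol 12.5.2.9 also treats a return at lower stage as a recurrence, in an exploratory comparison.

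Protocol 12.5.2.3 defines disease-free survival (DFS) through recurrence or progression and redefines neither term. Protocol 3.1 and the synopsis say that disease-free status is analysed under the definitions of section 10.1.

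**The concern.** One endpoint name carries two event definitions, and no text says which prevails. Protocol 3.4.2 lists the proportions with recurrence and with progressive disease from 3 to 24 months as secondary endpoints. Protocol 12.5.2 analyses the secondary parameters by Kaplan-Meier methods, and 12.5.2.1 and 12.5.2.2 are its only entries for these two events. An analyst working from that section would count fewer events of the types above than one working from the SAP, and both would label the result the same way. With about 25 patients per arm, a few reclassified events would visibly move a Kaplan-Meier estimate.

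**Working it through.** This is a comparison of definitions. No planned number depends on 12.5.2.1 or 12.5.2.2. The nearest design figure, 80% power, belongs to 1-year DFS: an exact one-sided Fisher test at 0.10, with 60% versus 90% and 23 evaluable per arm, gives 80.8%. That figure is reproduced and not in dispute.

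**Step 1. Run possible returns through each definition.** SAP section 7 ranks Ta < TIS < T1 and low grade < high grade.

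| Screening to return | 12.5.2.1: same stage and grade? | 12.5.2.2: greater stage? | Section 10.1 and SAP 7.2 |
|---|---|---|---|
| T1 to Ta or CIS | no | no | recurrence |
| CIS to Ta | no | no | recurrence |
| High-grade Ta to low-grade Ta | no | no | recurrence |
| Low-grade Ta to high-grade Ta | no | no | progression |
| High-grade Ta to CIS | no | yes | neither |

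The first four rows are events under section 10.1 and the SAP but under neither 12.5.2 definition. The last row runs the other way. Section 10.1 counts a stage increase below T2 only when it reaches T1, and CIS ranks above Ta, so this return is not at the same or a lower stage either.

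**Step 2. Who is exposed.** The lower-stage or lower-grade gap can touch only patients who enter above low-grade Ta, that is, high-risk patients. It is not confined to T1 entrants. The grade gap can touch only patients who are low-grade at screening. That includes the whole intermediate-risk stratum, because inclusion criterion 3 defines it as Ta low-grade.

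**Step 3. What happens to a missed event.** A patient who stays on treatment may later have a same-extent return, which is then counted, but late. Under Protocol 6.3, a patient who stops treatment with recurrent or progressive disease has no further disease assessments. If the SAP 7.2 censoring rule (last disease assessment) is applied to the narrow definition, that patient is censored at about the time of the actual recurrence, which is informative censoring.

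**Step 4. Size.** Let R be the proportion with recurrence by a given time under section 10.1. Let s be the share of those patients whose only return by then is at a lower stage or grade. Ignoring censoring, the narrow definition counts R × (1 − s). The documents give neither R nor s, so no figure follows.

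**The case against.** The best defence is that the SAP settles the matter. Protocol 12.1 leaves the exact methods to the SAP, the SAP states the wide definitions in two places, and the protocol's revision history records an intent to bring section 12 into line with it. The narrow sentences therefore look like a drafting remnant rather than a competing analysis. SAP 2.1 also attaches the wide definition directly to the recurrence proportions that the protocol lists. The same rule would apply in every arm, so no between-arm bias is shown, and SAP 5.5 limits secondary endpoints to estimates with confidence intervals. Most of this stands: an analyst who follows the SAP loses nothing. What it does not supply is a rule for the conflict, because a different event definition is more than a detail of method.

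Three stronger readings are tempting, and the documents do not support them.

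- **That the primary endpoint loses events.** If 20% of events were dropped in every arm (an assumption), the design rates would become 1 − 0.40 × 0.80 = 68% and 1 − 0.10 × 0.80 = 92%, and Fisher power at 23 per arm would fall from 80.8% to 69.1%. But Protocol 3.1 and the synopsis tie disease-free status to section 10.1, which requires no evidence of disease. The narrow wording does not reach this endpoint as written.
- **That the same events necessarily drop out of time-to-event DFS.** Section 12.5.2.3 follows the narrow definitions but does not adopt them. Which meaning applies is open.
- **That a 40% recurrence proportion would be reported as 32% to 24%.** The arithmetic is 0.40 × 0.80 = 0.32 and 0.40 × 0.60 = 0.24, but both inputs are assumptions. If 40% is taken as the complement of 60% control DFS, it also contains progression and death. The 20% to 40% share has no source. Low-grade Ta entrants cannot return lower, and later same-extent events would still count.

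**Conclusion.** The contradiction is real and rests on the wording alone. Read literally, the protocol's time to recurrence and time to progression omit returns at lower stage or grade and low-grade Ta returning as high-grade Ta, and would differ from the SAP's results of the same name. The consequence is limited to secondary endpoints and arises only if section 12.5.2 is followed in place of section 10.1 and the SAP. Primary 1-year DFS is not shown to be affected, and time-to-event DFS in 12.5.2.3 is ambiguous rather than shown to be wrong. The number of events at stake cannot be derived from the documents.

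**What to change.** - Have Protocol 12.5.2.1, 12.5.2.2 and 12.5.2.3 use recurrence and progression as defined in section 10.1, which matches SAP 7.2.
- Keep the restricted recurrence definition (screening extent or greater) only as the exploratory repeat in SAP 7.2.
- In the same edit, state in section 10.1 and SAP 7.2 in which category a return from Ta to CIS is counted. A bare cross-reference to 10.1 would drop the high-grade Ta to CIS return that 12.5.2.2 now captures.
- Reconcile 12.5.2.3 with section 12.1 on death. Section 12.1 makes death a time-to-event DFS event, while 12.5.2.3 leaves it out, as does the DFS definition in SAP 7.2.

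The cost is a wording amendment to both documents. Section 10.1 already has stage recorded at each recurrence or progression so that events can be sorted by stage and severity, so no new data are needed.

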##### **12.5.2.2 Time to Progression**

Defined as the time from randomization to progression of disease to a greater stage.

##### **12.5.2.3 Disease-Free Survival**

Defined as time from randomization to recurrence or progression

##### **12.5.2.4 Overall disease-free survival**

Overall DFS is defined as the interval between the date of disease recurrence, progression, or death (whichever occurs first) and the date of randomization/treatment assignment (Arm 4) for patients without CIS. For patients with CIS at screening who have persistent disease at 6 months, the date of disease persistence will be defined as the date of randomization/treatment assignment (Arm 4) (i.e. DFS = zero).

Patients with CIS at screening who are disease-free by 6 months will have their overall DFS interval calculated between the date of disease recurrence, progression, or death (whichever occurs first) and the earliest date that the patient was determined to be disease-free. Patients will be censored at the last time of contact if recurrence, progression, or death has not been confirmed at the time of the analysis. Overall DFS will be analyzed using a log-rank test with a term for treatment assignment. In addition, Kaplan-Meier curves will be produced separately for each treatment group. The weighted log rank test will also be applied in an exploratory manner.

In a supporting analysis, a simple Cox proportional hazards model with treatment group as the sole independent variable will be built in order to estimate the hazard rate (HR) and 95%CI for overall DFS between the low and high dose vesigenurtacel-L groups relative to the control. A HR of less than one will provide initial evidence of a favorable outcome with vesigenurtacel-L. These analyses will be completed for the ITT and Per-Protocol populations.

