Statistical methods:	
Patients will be randomized centrally using a stratified block design according to risk of recurrence (strata: high vs. intermediate risk) and CIS (strata: yes vs. no) for Arms 1-3. Patients who will not receive BCG will be consecutively allocated into a fourth arm consisting of vaccine monotherapy. Efficacy comparisons between the monotherapy arm and any of the randomized arms will remain exploratory. However, safety and point estimates with appropriate measures of variance (SD, 95% CI) for the efficacy parameters will be estimated.
 
For the randomized portion, the sample size is based on the hypothesis that the addition of vesigenurtacel-L to BCG versus BCG alone will improve disease-free survival at one year. The sample size will be 75 patients randomized into two experimental groups consisting of BCG plus low dose vesigenurtacel-L (<math>1 \times 10^6</math> cells per dose) and BCG plus high dose vesigenurtacel-L (<math>1 \times 10^7</math> cells per dose) and to a control group consisting of BCG plus placebo (final allocation = 25 vs 25 vs. 25) to provide 46 events in the experimental groups and 23 events in the control group. By assuming an alpha of 10% (one tailed), the randomized portion should have an 80% power to detect a 30% reduction in the risk of disease recurrence, progression, or death (control = 60% disease-free and alive vs. 90% in vesigenurtacel-L groups) at one year. There will be no adjustment for multiplicity in the comparison of the primary endpoint between the experimental groups and the control.
 
The primary endpoint (proportion of patients alive and disease-free at one year) between the two experimental groups and the control will be compared using Fisher's exact test and presented as odds ratios (OR) with 95% confidence intervals (CI) relative to the control group. ORs will be generated via a simple logistic regression model with one year disease-free survival as the dependent variable and group as the sole independent variable (low dose and high dose vesigenurtacel-L vs. control). If the analysis of the primary endpoint does not suggest any dose response effect between the two vaccine arms, an exploratory analysis will be conducted where the two vaccine arms will be pooled and compared to the control arm for the primary endpoint (proportion of patients alive and disease-free at one year). The outcome will be presented as OR with 95% CI relative to the control group.
 
Binary secondary endpoints will be presented as ORs with appropriate 95% CI.
 
For the time to event endpoints (i.e. overall DFS and OS), survival curves will be generated by the method of Kaplan-Meier and compared with the log-rank test. In an exploratory analysis, the weighted log rank test will also be used. The weighted log rank preserves the statistical power that is lost due to the lag time effect in efficacy with immunotherapeutic agents. In a supporting analysis, a simple Cox proportional hazards model with treatment group as the sole independent variable will be built in order to estimate the hazard rate (HR) and 95% CI for DFS between the low and high dose vesigenurtacel-L groups relative to the control.
 
In an exploratory analysis, patients experiencing an immune response in all four treatment arms will be compared to those who did not experience an immune response. The analysis will include a univariate comparison of patient and clinical variables at baseline

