The objective of the phase 2 study is to compare 1-year disease free survival of two doses of HS-410 + BCG versus BCG + placebo in patients with non-muscle invasive bladder cancer who have undergone TURBT. Given the phase 2 exploratory nature of the study, the overall level of significance will be 0.10, using a one sided test with no adjustment for multiplicity, 75 patients will be randomized in a 1:1:1 (low dose HS-410 plus BCG and high dose HS-410 plus BCG vs. plus BCG + placebo) ratio to yield 69 evaluable (23 patients per arm). 25 patients will be enrolled into the monotherapy arm. Under the assumption that the one-year disease-free survival rate in the control is 60%, the study will have an 80% power to detect a 30% absolute difference between the two experimental groups and the control. Patients will be followed for three years after the last patient has been enrolled and patients will be obtained from approximately 20 participating centers.

5 Statistical Considerations

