7.1 Primary Efficacy Analysis

The primary efficacy parameter is 1 year DFS and will be conducted on the ITT population. It will be calculated as the proportion of patients in the experimental groups and the control who remain disease free at 1 year. Hypothesis testing on the primary endpoint will be done one-sided at a level of significance of $\alpha = 0.10$ using Fisher's exact test. The absolute difference in proportions, as well as the odds ratio, with the associated 95% confidence intervals will also be presented.

The following rules will be used to determine whether a patient is disease free at 1 year or not

- If a patient has a recurrence before day 394 (ie day 366+28 days) or has dropped out of the study before day 394, then the patient is considered to be not disease free at 1 year.
- If a patient is shown to be free from disease on day 366 +/- 28 days, then the patient is considered to be disease free at 1 year.
- If a patient has no recurrence before day 338 (ie day 366-28 days) and after day 394 (day 366+28 days), then the patient is considered to be disease free at 1 year.

If the analysis of the primary endpoint does not suggest any dose response effect between the two vaccine arms, an exploratory analysis will be conducted where the two vaccine arms will be pooled and compared to the control arm for the primary endpoint (proportion of patients alive and disease-free at one year). The outcome will be presented as OR with 95% CI relative to the control group.

In an additional exploratory analysis, the proportion of patients whose disease has recurred to a lower stage than at screening and the proportion of patients whose disease has recurred to the same extent (or greater) as at screening will be compared between the experimental and control groups and presented as an OR with 95% CI.

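### Protocol 12.5.2.4 treats any hazard ratio below one as initial evidence of benefit, a standard that an ineffective vaccine meets half the time per dose and two times in three for at least one dose

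*Protocol*

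**What the plan says.** Protocol 12.5.2.4 plans a log-rank test and Kaplan-Meier curves for overall disease-free survival, and then adds: "In a supporting analysis, a simple Cox proportional hazards model with treatment group as the sole independent variable will be built". The model gives a hazard ratio with a 95% CI "between the low and high dose vesigenurtacel-L groups relative to the control", so there are two contrasts against one placebo arm. The next sentence is the one at issue: "A HR of less than one will provide initial evidence of a favorable outcome with vesigenurtacel-L". The analyses are run in both the ITT and the Per-Protocol populations.

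The protocol synopsis describes the same Cox model without that sentence. The SAP does not contain it either. SAP 7.2 says "the treatment effect will be estimated using Cox proportional hazards model", and allows log-rank inference where appropriate. SAP 5.5 calls the trial exploratory, restricts p-values to the primary comparison of the two doses with placebo, and has secondary endpoints reported as estimates with 95% CI.

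For the primary endpoint the plan does set an error rate. SAP section 4 says "the overall level of significance will be 0.10, using a one sided test with no adjustment for multiplicity", and SAP 7.1 says "Hypothesis testing on the primary endpoint will be done one-sided at a level of significance of" 0.10, using Fisher's exact test.

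**The concern.** The sentence fixes in advance how a result will be described, and it uses only the side of 1 on which the estimate falls. With no effect, an estimate falls on either side about equally often, so the description carries very little information. Two doses share one control, which gives two chances to meet the standard, and the Per-Protocol repeat adds another.

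What is at stake is the reporting of a secondary result. If the primary Fisher test missed, a hazard ratio of 0.95 with a wide interval would still meet the protocol's stated standard for initial evidence of a favourable outcome.

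**Working it through.** **Inputs from the documents.** Allocation is 1:1:1 ("final allocation = 25 vs 25 vs. 25", protocol synopsis), with 23 evaluable per arm ("ratio to yield 69 evaluable (23 patients per arm", SAP section 4). One-year disease-free survival is taken as 60% on control and 90% on vaccine. The primary test is one-sided at 0.10. Follow-up lasts three years after the last enrolment (protocol 12.6.2).

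**Assumed, not in the documents.** Exponential survival, and individual follow-up of 3 to 4 years (3.5 in the formulas) unless stated otherwise.

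**1. The plan's own figure.** The documents give no error rate for the hazard-ratio standard. The nearest stated figure is 80% power for the primary test. Exact enumeration of the one-sided Fisher test at 0.10, 23 vs 23, 60% vs 90%, gives 80.8%, so it reproduces. With 60% in both arms, that test rejects 5.1% of the time per dose (5.7% with 25 per arm).

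**2. No effect, one dose.** Swapping the dose and placebo labels changes the sign of the log hazard ratio and leaves its distribution unchanged. Hence P(HR < 1) = 1/2, apart from exact ties.

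**3. No effect, at least one dose.** Neither dose has HR < 1 only when placebo has the lowest estimated hazard of three exchangeable arms, which has probability 1/3. Hence P(at least one HR < 1) = 1 − 1/3 = 2/3. As a cross-check, the shared control gives the two log hazard ratios a correlation of 0.5, so P(both ≥ 1) = 1/4 + arcsin(0.5)/(2π) = 0.2500 + 0.0833 = 0.3333. Treating the doses as independent would wrongly give 1 − 0.25 = 75%.

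**4. Simulated three-arm Cox fits, no effect, 60% at one year.**

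| Setting | HR < 1, each dose | HR < 1, at least one |
|---|---|---|
| 25 per arm, 3-4 years | 50.1%, 50.9% | 67.2% |
| 25 per arm, 1 year, 3-monthly visits | 50.7%, 52.0% | 67.8% |
| 23 per arm, 3 years, 3-monthly visits | 51.4%, 50.7% | 67.5% |

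**5. A harmful vaccine, true HR 1.25, 25 per arm.**
- Control hazard: −ln 0.6 = 0.5108 per year. Vaccine hazard: 0.5108 × 1.25 = 0.6385.
- Expected control events: 25 × (1 − exp(−0.5108 × 3.5)) = 20.8.
- Expected events per vaccine arm: 25 × (1 − exp(−0.6385 × 3.5)) = 22.3.
- SE of the log hazard ratio: √(1/20.8 + 1/22.3) = 0.305.
- One dose: Φ(−ln 1.25/0.305) = Φ(−0.732) = 23%.
- Correlation: (1/20.8)/0.0928 = 0.517, so both doses meet the standard with probability 11.0%. Either dose: 2 × 23.2% − 11.0% = 35%.

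Simulations gave 23-25% per dose and 36-38% for either dose. At a true HR of 1.5 they gave about 9% and 15%.

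**6. The alternative standard: upper limit of the planned 95% CI below 1.**
- No effect: nominally 2.5% per dose. Simulated over the settings in step 4, it was 1.8-2.5% per dose and 3.4-4.5% for at least one.
- True HR 1.25: simulated 0.4% and 0.7%.
- With about 20.8 events per arm the SE is √(2/20.8) = 0.310, so the estimate must be below exp(−1.96 × 0.310) = 0.54.
- Power per dose, 90% vs 60%: HR = ln 0.9/ln 0.6 = 0.206, 7.7 vaccine events, SE 0.422, Φ(1.579/0.422 − 1.96) = 96%.
- Power per dose, 80% vs 60%: HR = ln 0.8/ln 0.6 = 0.437, 13.6 vaccine events, SE 0.349, Φ(0.828/0.349 − 1.96) = 66%.

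**The case against.** The strongest reply is that this is a descriptive sentence and not a decision rule. The protocol labels the Cox model supporting and the evidence only initial. It plans the 95% CI in the preceding sentence and a log-rank test in the same section. No success criterion, dose choice or continuation decision in either document refers to a hazard ratio below one, and the optional Week 25 analysis in protocol 12.1 does not mention it. Protocol 12.1 sends the reader to the SAP for exact methods, and SAP 5.5 and 7.2 treat secondary endpoints as matters of estimation.

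Most of this stands, and it limits the weight of the point. It does not rescue the sentence. A planned interval is no safeguard if the stated interpretation does not depend on it, and an exploratory aim justifies a lenient threshold but not the absence of one. Had the sentence said only that a ratio below one favours the vaccine in direction, there would be nothing to correct.

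A reader might infer that the standard lets the trial be declared positive, that it weakens the primary error rate, or that the SAP applies it too. The documents support none of these: the primary test has its own alpha, and the SAP has no such sentence.

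**Conclusion.** The point holds as a limited but real error of interpretation in one protocol sentence. With no effect, the standard is met about 50% of the time per dose and about two times in three for at least one dose. These figures follow from randomisation and the shared 1:1:1 control. They do not depend on the event rate or censoring pattern beyond small-sample error, and they do not count the Per-Protocol repeat. For comparison, the primary Fisher test rejects about 5-6% of the time per dose when both arms are at 60%.

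The figures at a true hazard ratio of 1.25 (about 23-25% per dose and 36-38% for either) do rest on assumed exponential survival and follow-up length. They also ignore the special time origins for patients with CIS in 12.5.2.4. They are illustrative.

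The primary analysis, its alpha and the sample size are unaffected.

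**What to change.** **Preferred.** Delete the sentence from protocol 12.5.2.4 and report each hazard ratio with its 95% CI only. This brings the section into line with the synopsis and SAP 5.5. No SAP change is needed, because the SAP has no such sentence to remove.

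**If an interpretive statement is kept,** replace it with wording such as: *A hazard ratio below 1 indicates direction only. A dose will be described as showing evidence of benefit on overall DFS only if the upper limit of its 95% CI is below 1; no adjustment is made for the two doses.* This uses the interval already planned.

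A looser bound, such as the upper limit of an 80% CI, is not recommended. It would act as an extra test of a secondary endpoint, against the policy in SAP 5.5, and would still label an ineffective vaccine favourable for at least one dose in about 17% of trials.

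**Cost.** One protocol sentence, with no new data and no change to the primary analysis. A weak favourable estimate can no longer be called evidence. Under the alternative wording, per-dose power is about 96% at the design effect (90% vs 60%) but about 66% at 80% vs 60%, assuming a constant hazard ratio. It would be lower if the vaccine effect is delayed, as protocol 12.1 anticipates.
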